3 PROTOCOL SYNOPSIS

3.1 Purpose:

This protocol seeks to analyze patient outcomes of the standard of care, monitored group exercise regimen of high-load resistance training and functional exercises with compound movements under close supervision on women who have been treated for breast cancer.

Primary Objective

- 1 Determine safety and feasibility measured by exercise compliance.

Exploratory Objectives

- 1 Determine changes in functional mobility testing changes at baseline, throughout, post-exercise assessment and 1 year after exercise assessment.
- 2 Determine quality of life at baseline, throughout, and post- exercise assessment
- 3 Determine changes in strength and load lifted at baseline, throughout, post-exercise assessment, and 1 year after exercise assessment.
- 4 Determine changes in resting metabolic rate at baseline, throughout, post- exercise assessment, and 1 year after exercise assessment.
- 5 Determine changes in body composition at baseline, throughout, post- exercise assessment and 1 year after exercise assessment, including body mass, fat mass, fat-free mass, % fat, and % fat-free mass.

Hypotheses

In this study, we hypothesize that an observed exercise regimen utilizing high-load resistance training initiated during or after cancer treatment is safe and feasible in women and may improve functional mobility, body composition, and resting metabolic rate.

3.2 Background and Significance:

Obesity is a risk factor for both breast cancer and disease recurrence after treatment.¹ Furthermore, weight gain during and after treatment for breast cancer is associated with a higher risk of recurrence, distant metastases, and death.² Yet, most women gain significant weight during and after breast cancer treatment, potentially compromising outcomes.

Contrary to these findings, activity levels have been repeatedly associated with a lower risk of breast cancer incidence, improved outcomes after breast cancer treatment, and improved breast cancer-specific and overall survival.³ The majority of breast cancer survivors do not meet adequate daily activity level recommendations, potentially compounding issues with weight gain during and after breast cancer treatment.⁴ As a result, attempts are underway to both quantify and increase activity levels during treatment and survivorship.⁵ Furthermore, and based on these findings, several areas of

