6. PATIENT ASSESSMENTS

Table 1: Participant Assessments

Assessment	Screening	Baseline Assessments (Prior to Program)	During Exercise Program	At Exercise Program Completion	1 Year After Exercise Program Completion
Consent	X				X ^f
History/Physical	X				
Weight, height, and BMI	X			X	X
Body Composition Assessment ^a		X		X	X
Resting Metabolic Rate Assessment		X		X	X

QOL and Exercise Forms ^b		X		X	X
Strength Assessment ^{c,d}		X	X	X	X
Mobility Assessment ^c		X		X	X
Compliance ^e			X		

- a To calculate lean and fat mass and percentages, and total energy expenditure (kcal/day) SOC
- b EQ-5D-5L, and Leisure-Time Exercise Questionnaire SOC
- c Functional Mobility Survey and Y-balance test, includes grip strength SOC
- d Will also occur periodically throughout program to adjust exercise regimen SOC
- e Attendance collected at each workout
- f Verbally reconsent to use SOC data for research purposes

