6.2 Study-Specific Assessment

a. Baseline Examinations

If not already collected during screening, baseline complete history and physical, weight, height, and BMI will be collected as SOC. In addition, baseline QoL forms, and the Leisure-Time Exercise Questionnaire that are SOC, will be administered. It will take 15-20 minutes to complete both questionnaires. All baseline assessments will be performed at the Exercise Oncology Center as per SOC, and must be collected within the 3 months prior to starting the exercise regimen. No laboratory draws for this protocol are required.

b. Baseline Metabolic, Body Composition, Strength, and Mobility Testing

Prior to initiation of the exercise regimen, each participant will undergo body composition analysis via an InBody 970. InBody testing is noninvasive and requires no ionizing radiation. The individual simply stands on the machine while holding handles. An ultrasound will also be used to measure muscle and adipose tissue thickness to provide additional metrics for body composition. This will be performed via a traditional ultrasound and software (BodyMetrix) will calculate

muscle mass, fat mass, and body composition metrics. More information is supplied in Appendix VI. Both also supply resting metabolic rate calculations. Functional movement assessments will be performed at this visit as well, and takes approximately 10 minutes.

Resting metabolic rate may also be assessed per SOC at this session via a VO2 Master device (VO2 Master Health Sensors Inc., British Columbia, Canada), where the individual will breathe into the device for several minutes at a time. The total test takes less than 15 minutes. The test is noninvasive and measures respiratory airflow and oxygen consumption in order to calculate resting metabolic rate. Alternatively, the InBody machine and ultrasound can be utilized to measure metabolic rate as well. Additional testing with this device is at the discretion of the staff as per SOC. Grip strength will be assessed via a Jamar Hand Dynamometer Grip Strength Measurement Meter bilaterally at the neutral position and with the arm of the head.

These tests are part of the SOC exercise regimen and workup and no additional costs will be associated with these procedures.

6.3 Exercise Period:

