The exercise program will last three months. The initial exercise schema was developed by the PI and exercise personnel. Throughout the exercise program, participants will continuously be assessed via load lifted calculations and observations of exercise mechanics, both of which will impact increases in load and exercise difficulty during the program, as per SOC.

6.4 Follow-up Period:

There will be no follow-up once an individual completes the study.

6.5 Early Withdrawal of Subject(s):

If at any time the constraints of this protocol are detrimental to the patient's health and/or the patient no longer wishes to continue in the study, the patient will be removed from the protocol follow-up. In this event the reason(s) for discontinuation of study participation will be noted by the PI in the record. Data acquired up until that point will be retained for analyses.

There will be a SOC follow up assessment 1 year after the completion of the exercise program. The data from the SOC assessment will be used for research purposes.

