Subject names or identifiers will not be used in reports, presentations at scientific meetings, or publications in scientific journals.

Data Collection:

The following data will be stored in the secure database:

- Age
- Diagnosis
- Weight, height, and BMI
- Comorbid medical conditions
- Surgical procedure for breast cancer or orthopedic procedures
- Type of hormonal therapy
- Body composition at start/completion (body fat percentage, % fat-free mass, fat mass, fat-free mass, body mass)
- Resting metabolic rate at start/completion
- Exercise details (specific exercise, repetitions, weight, load lifted)
- FMS and Y-balance test
- Grip strength at start/completion
- QOL forms (EQ-5D-5L)
- Godin Leisure-Time Exercise Questionnaire
- Adherence rates (percentage classes)
- Assessments that are SOC

10.5 Protocol Amendments:

All protocol amendments must be initiated by the Principal Investigator and approved by the IRB prior to implementation. IRB approval is not required for protocol changes that occur to protect the safety of a subject from an immediate hazard. However, the Principal Investigator must inform the IRB and all other applicable regulatory agencies of such action immediately.

10.6 Records Retention:

The Principal Investigator will maintain study-related records for the longer of a period of at least six years after study completion, or per AHN policy, whichever is more strict.

APPENDICES

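### Do the differing visit lists and the unnamed measurement source for resting metabolic rate (exploratory objective 4) call for a change to the plan?

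*Combined protocol and SAP*

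**What the plan says.** **Objective and hypothesis (section 3.1).** Exploratory objective 4 reads "Determine changes in resting metabolic rate at baseline, throughout, post- exercise assessment, and 1 year after exercise assessment". The hypothesis is that the regimen is safe and feasible and "may improve functional mobility, body composition, and resting metabolic rate".

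**Schedule (section 6, Table 1).** The row "Resting Metabolic Rate Assessment" is marked at baseline, at program completion and 1 year later. The cell for the exercise period is empty. Section 6.3 describes what is assessed in that period: "participants will continuously be assessed via load lifted calculations and observations of exercise mechanics". RMR is not mentioned there.

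**Data list (section 10.4).** One item is "Resting metabolic rate at start/completion". The list ends with "Assessments that are SOC". Section 6.5 says of the 1-year visit: "The data from the SOC assessment will be used for research purposes".

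**Source (section 6.2b).** Every participant has an InBody measurement, and ultrasound is also planned for body composition. The text then says "Both also supply resting metabolic rate calculations". A VO2 Master test, which works from oxygen consumption, may be added. InBody and ultrasound are then offered as alternatives for obtaining metabolic rate.

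**Analysis (section 7.3).** All metabolic measurements get a change from baseline, tested by a paired t-test or a Wilcoxon signed-rank test. No RMR source is named.

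**The concern.** Two things look wrong.

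First, three parts of the plan describe the RMR visits differently: four time categories in the objective, three in Table 1 and two in the RMR item of section 10.4. Taken literally, the objective asks for a result during the program that no section schedules.

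Second, a participant could have two RMR values at baseline, or three with VO2 Master, while Table 1 has one RMR row and section 10.4 one RMR item. The sources differ in kind: InBody and ultrasound calculate RMR, while VO2 Master derives it from measured oxygen consumption. If devices were mixed between visits, a change of device could pass for a change in metabolism. If they were not mixed, someone could still choose the most favourable of several RMR changes once results were known. RMR is one of three outcomes the hypothesis expects to improve, so a reader would want to know which number bears on it.

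**Working it through.** The plan states no sample size, significance level or effect size for RMR, so there is no figure of its own to reproduce. The check sets the passages side by side and then sizes the worst case.

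**1. Visits.**

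| Place | Baseline | During program | Completion | 1 year |
|---|---|---|---|---|
| Objective 4 | yes | yes, undated | yes | yes |
| Table 1, RMR row | yes | blank | yes | yes |
| 10.4, RMR item | yes | no | yes | not named |

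- The missing 1-year entry in 10.4 is not a firm conflict. The closing item of that list covers standard-of-care assessments, and sections 3.6, 5.3, 6.5 and 10.2 all provide for research use of the 1-year data (10.2 subject to reconsent). The body composition item in 10.4 uses the same start/completion shorthand, although Table 1 marks that row at 1 year too.
- That leaves one word, *throughout*. It names a period, not a visit. It also appears in objectives 1, 2 and 5 (mobility, quality of life, body composition), whose Table 1 rows have the same blank cell. Of the measured outcomes, only strength is marked during the program. This is repeated stock wording, not a lost RMR visit.
- Effect on results: the Table 1 schedule gives 3 − 1 = 2 changes from baseline per source, at completion and at 1 year. Deleting *throughout* would alter neither.

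**2. Sources.** On the fullest reading of 6.2b there are 2 baseline values per participant, and 3 where VO2 Master is used. Possible RMR changes over the Table 1 visits are (3 − 1) × 2 = 4 or (3 − 1) × 3 = 6, against 2 with a single source. The two-value count is itself an inference: the text says what the devices can supply, ultrasound is there for body composition, and nothing says its RMR value is recorded.

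**3. Worst case from choosing a source afterwards.** Take one visit, no true change, like-with-like paired tests, and a two-sided 5% level (assumed, since 7.3 states none). The chance that at least one of k sources reaches p < 0.05 is as follows.

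- Identical sources: 5.0%.
- Independent sources: 1 − 0.95^k. For k = 2, 1 − 0.9025 = 9.75%. For k = 3, 1 − 0.857375 = 14.3%.
- Simulation with n = 40, multivariate normal changes and 200,000 runs per case: at correlation 0.8, 7.9% (k = 2) and 10.0% (k = 3); at 0.95, 6.4% and 7.4%.

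The correlation is that between within-person changes on different devices. It is not in the documents, so 0.8 to 0.95 is only an illustrative range. The three-source figures also assume VO2 Master in every participant, which 6.2b does not promise.

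**The case for a change.** The strongest case for acting is that RMR is named in the hypothesis, no section identifies the analysed value, and a sentence in 7.3 would cost almost nothing. Pairing like with like prevents mixing of devices but still leaves two or three RMR changes. Source records can show which device was used, not which was meant to answer objective 4. Section 6.2b does not imply a ranking either: VO2 Master is an optional addition, and the other two are then called alternatives.

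Much of this stands. The source is not named, and RMR during the program is not scheduled. What does not follow is that the plan must change. The sentence one would add to 7.3 could not itself name a device, because the documents give no basis for choosing; it would leave a blank for the sponsor. What it could prescribe, using the same source at both visits and reporting any other source separately, is what a competent analyst does under a paired test of change from baseline. Nothing in the plan shows that devices will be mixed or that one result will be picked.

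Nor does selection have a prize here. Section 7.3 sets no threshold or success claim for any exploratory outcome, and it tests many of them without multiplicity control. An extra 1.4 to 2.9 percentage points (6.4% − 5.0% and 7.9% − 5.0%, two sources, illustrative correlations) on one nominal p-value does not alter how such results should be read.

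**Conclusion.** No change to the plan is called for. Two narrow facts hold: *throughout* in objective 4 has no matching RMR assessment in Table 1, and no section names the RMR source to be analysed. The first is loose wording shared by four exploratory objectives and alters no result. The second is a gap that analysts fill sensibly, by pairing within device and stating which device each RMR change comes from, with calculated and oxygen-based values kept apart.

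The size is small. Table 1 yields 2 RMR changes per source, and the worst-case inflation from choosing between sources at one visit runs from 5.0% to 9.75% with two and to 14.3% with three. The upper ends are ceilings that need independent sources, an assumed 5% level, every source in every participant, and a choice made after seeing results. The 75%-attendance endpoint, the 0.56 lower-bound rule and the sample of 40 do not depend on RMR. The conclusion would be different if RMR carried a confirmatory claim or a success threshold, or if records showed devices switched between a participant's visits.

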APPENDIX VI: Body Composition Testing

All participants will undergo body composition testing via the InBody 970 model.

InBody testing will take place at Exercise Oncology Center during initial assessment. The InBody test takes about 3 minutes. Participants are required to abstain from food, drink or exercise prior to the test and will be fasted overnight. During the exam, they merely stand quietly on the machine

The InBody 970 is a bioimpedance analysis device, which utilizes electric currents to calculate a phase angle and resulting body composition metrics. Users stand barefoot on a device that is similar to a traditional scale, and they hold one handle for each hand, with the feet and hands touching metal electrodes. The device sends a low-dose electrical current and measures the change in phase angle. There is no risk to the user.

An ultrasound will also be used to measure muscle and adipose tissue thickness to provide additional metrics for body composition. This will be performed via a traditional ultrasound and software (BodyMetrix) will calculate muscle mass, fat mass, and body composition metrics.

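### Resting metabolic rate may be taken from InBody or ultrasound calculations, which rest on body composition signals, so a change in it cannot show a metabolic effect separate from objective 5

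*Combined protocol and SAP*

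**What the plan says.** Section 3.1 lists two separate exploratory objectives. Objective 4 is: "Determine changes in resting metabolic rate at baseline, throughout, post- exercise assessment, and 1 year after exercise assessment". Objective 5 begins: "Determine changes in body composition at baseline, throughout, post- exercise assessment and 1 year after exercise assessment", and its variables include fat mass and fat-free mass. The hypothesis also lists them as distinct gains: the regimen "may improve functional mobility, body composition, and resting metabolic rate".

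Section 6.2b describes three devices. Of the InBody and the ultrasound, which are there for body composition, it says: "Both also supply resting metabolic rate calculations". It then says RMR *may* also be assessed with the VO2 Master, which senses airflow and oxygen uptake. It adds: "Alternatively, the InBody machine and ultrasound can be utilized to measure metabolic rate as well". Appendix VI describes the InBody as a bioimpedance device, "which utilizes electric currents to calculate a phase angle and resulting body composition metrics", and the ultrasound as measuring the thickness of muscle and fat.

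Table 1 gives RMR its own row at baseline, completion and 1 year, but names no device. The data list in section 10.4 has one RMR item with no field for its source. Section 7.3 tests each measure's change from baseline with a paired t-test or a Wilcoxon signed-rank test. No section limits objective 4 to oxygen-based values or requires the same method at both visits.

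**The concern.** Within 6.2b the same two outputs are first calculations and then an acceptable way to measure metabolic rate. The wording matters because the measured route is optional and the source is not recorded. A trial that follows the plan to the letter could answer objective 4 entirely from calculated values. A gain in lean mass would then be reported under objective 5 and could reappear under objective 4 as a gain in metabolic rate, as if it were separate evidence. Choosing one device for everyone would not cure this if the device chosen were the InBody or the ultrasound.

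**Working it through.** The documents give no effect size, SD, power or significance level for RMR, so there is no planned figure to reproduce. The check compares the descriptions of the devices and then follows the consequence through the section 7.3 tests.

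**1. What each device senses (6.2b, Appendix VI)**

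| Device | Signal | RMR obtained from |
|---|---|---|
| InBody 970 | electrical impedance | calculation, equation not given |
| Ultrasound with BodyMetrix | tissue thickness | calculation, equation not given |
| VO2 Master (optional) | airflow and oxygen uptake | calculation from measured oxygen |

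All three calculate RMR. The difference lies in the signal: only the third is a metabolic one. Height, weight or age may also enter the first two equations, but none of these is a metabolic measurement.

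**2. Formula linear in fat-free mass (FFM) alone, same device (assumed form)**

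If RMR = a + b × FFM with b > 0, then ΔRMR = b × ΔFFM. The paired t statistic is mean(Δ) ÷ (SD(Δ) ÷ √n). Multiplying every Δ by b scales the mean and the SD equally, so b cancels. The signed ranks do not change either.

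Illustration on one simulated data set, n = 40 (the target sample size in section 3.5; everything else assumed). Mean ΔFFM = 0.425 kg and SD = 0.892 kg, so t = 0.425 ÷ (0.892 ÷ √40) = 3.01.

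| Variable tested | Mean change | t | p (t-test) | p (Wilcoxon) |
|---|---|---|---|---|
| ΔFFM | 0.425 kg | 3.011 | 0.0045 | 0.0058 |
| ΔRMR, b = 10 kcal/day per kg | 4.25 kcal/day | 3.011 | 0.0045 | 0.0058 |
| ΔRMR, b = 20 | 8.50 kcal/day | 3.011 | 0.0045 | 0.0058 |
| ΔRMR, b = 30 | 12.75 kcal/day | 3.011 | 0.0045 | 0.0058 |

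The correlation of ΔRMR with ΔFFM is 1.0 in each case.

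**3. Fat mass (FM) added: ΔRMR = b × ΔFFM + c × ΔFM, b = 20 (assumed)**

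| c | Correlation of ΔRMR with ΔFFM | p for ΔRMR |
|---|---|---|
| 2 | 0.98 | 0.026 |
| 5 | 0.89 | 0.23 |
| 10 | 0.69 | 0.83 |

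The tests are no longer identical. However, the residual of ΔRMR given ΔFFM and ΔFM is zero in every row, so RMR adds nothing to the objective 5 variables. Under either form, a true change in metabolic rate with the formula's inputs unchanged gives ΔRMR = 0.

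**4. Chance of a significant RMR gain driven only by FFM**

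This uses the form in step 2, n = 40, df = 39 and two-sided 0.05 (assumed). The noncentrality is δ × √40, where δ is the mean FFM gain in SDs of change.

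| δ | Noncentrality | Probability |
|---|---|---|
| 0 | 0 | 0.025 |
| 0.3 | 1.90 | 0.46 |
| 0.5 | 3.16 | 0.87 |
| 0.8 | 5.06 | 0.9985 |

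No change in metabolism beyond composition is needed for any of these.

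**5. Mixed sources**

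With VO2 Master at baseline and a calculated value later, the difference is the true change plus the disagreement between methods at the later visit. The plan does not exclude such pairs.

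**The case against.** The strongest reply is that objective 4 asks for change in RMR, not RMR per kilogram or adjusted for lean mass. Section 3.2 treats RMR as proportional to muscle mass, so an estimate that follows lean mass fits the stated mechanism. This stands in part. A reader might infer that the InBody and ultrasound values say nothing about objective 4, and the documents do not support that: they are predictions of whole-body RMR. But a prediction assumes the link between muscle and metabolic rate and so cannot be evidence for it.

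A second reply is that the equations are unknown. That also stands. A reader might infer that the trial will report one finding twice, with correlation 1.0 and equal p-values. That needs a formula in fat-free mass alone, both variables from the same device, and no VO2 Master pairs. Setting ultrasound RMR against InBody fat-free mass, for example, would break the identity.

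Third, Table 1 footnote a lists as an aim of the body composition assessment: "To calculate lean and fat mass and percentages, and total energy expenditure (kcal/day) SOC". It is tempting to count this as a further flawed endpoint. Total energy expenditure is in no objective, and section 7 does not name it, so no planned conclusion depends on it.

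Finally, limiting a claim to VO2 Master pairs has its own weakness. The test is optional and, on the natural reading of 6.2b, used at staff discretion, so those women are a selected subset. That stands and belongs in the report.

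**Conclusion.** The concern holds in a limited form. Section 6.2b accepts as measurement two outputs that it also calls calculations and that come from devices with no metabolic signal. A change in such a value, tested under 7.3, cannot show a metabolic effect separate from objective 5.

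That the calculations depend largely or wholly on body composition is inferred from the signals described; the documents do not state it. The numerical results illustrate assumed formulas, and the argument does not depend on the slopes. How much of the trial is affected depends on how many women have VO2 Master values at both visits, which the documents do not allow one to estimate. For those women objective 4 stands on its own data.

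The objective is exploratory. The primary attendance endpoint and its success rule are untouched. The plan should still be corrected, because as written it permits a metabolic conclusion that the data could not carry.

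**What to change.** - In 6.2b, replace *measure* with *predict* for the InBody and ultrasound values.
- In the data list in 10.4, add the source of each RMR value.
- In 7.3, compute RMR change only where both visits used the same source. Report it separately by source, with the number of women for each.
- Base any claim of a change in metabolic rate distinct from body composition only on paired VO2 Master values, and state that this subset is chosen at staff discretion.
- Label InBody and ultrasound RMR as predicted from body composition, present it with objective 5, and do not count it as a separate benefit.

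No new procedure is needed, but one data field is added. The cost is that fewer women may support the RMR statement, and it may have to be dropped if few have paired VO2 Master tests.
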